4.5.13.9 Follow-up Visit (14-28 Days after Last Dosing)

The following will be performed at follow-up:

- Directed history (including review of AEs/SAEs, concomitant medications, oxygen use, and hospitalizations)
- Physical examination, vital signs, and weight
- Clinical laboratory assessments (hematology, serum chemistries)
- Estimating patient's further participation in the rollover study

4.5.13.10 Long-Term Follow-Up/ Rollover Study

Week 39 (± 2 weeks)

The following will be performed at Week 39:

- Physical examination, vital signs
- Clinical laboratory assessments (hematology, serum chemistries)
- Spirometry (FVC)
- 6MWT and Borg Scale
- Review AEs

Week 52 (± 2 weeks)

The following will be performed at Week 52:

- EQ5D questionnaire (should be performed before any other non-PRO assessments)
- *ECG. All ECGs are to be obtained prior to other procedures scheduled at that same time (e.g., vital sign measurements, blood draws) and should not be obtained within 3 hours after any meal.*
- Physical examination, vital signs
- Clinical laboratory assessments (hematology, serum chemistries)
- HRCT
- Spirometry (FVC)

Pirfenidone—F. Hoffmann-La Roche Ltd

- 6MWT and Borg Scale
- Review AEs

4.5.14 Samples for Research Biosample Repository

Not applicable as no samples will be stored in the study. All blood samples drawn for safety assessments will be destroyed immediately after analyzing.

4.6 PATIENT, TREATMENT, STUDY, AND SITE DISCONTINUATION

4.6.1 Patient Discontinuation

Patients have the right to voluntarily withdraw from the study at any time for any reason. In addition, the investigator has the right to withdraw a patient from the study at any time if it is considered to meet patients' interests best and approved by the Sponsor.

Reasons for withdrawal from the study may include, but are not limited to, the following:

- Patient withdrawal of consent at any time
- Any medical condition that the investigator or Sponsor determines may jeopardize the patient's safety if he or she continues in the study
- Investigator or Sponsor determines it is in the best interest of the patient for other reasons
- Protocol deviation (at Sponsor's discretion) (e.g. refusal to follow study requirements)

Generally poor compliance in the study will not be treated as a sufficient reason for patient's early discontinuation from the study. However, non-compliant patients cannot proceed in the rollover part of the study, where treatment with pirfenidone is continued in a routine clinical setting.

Every effort should be made to obtain information on patients who withdraw from the study. The primary reason for withdrawal from the study should be documented on the appropriate eCRF. However, patients will not be followed for any reason after consent has been withdrawn. Patients who withdraw from the study will not be replaced.

4.6.2 Study Treatment Discontinuation

Patients must discontinue study treatment if they experience any of the following:

- Pregnancy
- Unacceptable tolerability and personal safety profile (e.g. adverse events listed in [Section 5.1.2](#), or serious adverse events related to study treatment)

Pirfenidone—F. Hoffmann-La Roche Ltd

- Patient request or withdrawal of consent
- Patient's early discontinuation from the study (see [Section 4.6.1](#))
- Termination of the whole study by the Sponsor
- Lung transplantation

Patients who receive a lung transplant during the study will discontinue study treatment and the study itself.

If study treatment is discontinued, patients will complete a Follow-up Visit 14-28 days after the last dose of the study treatment. If applicable, discontinued patients should complete all scheduled study assessments and procedures through Week 26.

If early discontinuation of study treatment is being considered, it must be immediately reported by telephone to the Sponsor medical monitor or designee.

The primary reason for study treatment discontinuation should be documented on the appropriate eCRF. Patients who discontinue study treatment prematurely will not be replaced.

4.6.3 Study and Site Discontinuation

4.6.3.1 Study Discontinuation

The Sponsor has the right to terminate this study at any time. Reasons for terminating the study may include, but are not limited to, the following:

- The incidence or severity of adverse events in this or other ongoing studies of pirfenidone indicates a potential health hazard to patients.
- Patient enrollment is unsatisfactory.
- Administrative and regulatory reasons.

The Sponsor will notify the investigator if a decision to discontinue the study is made.

4.6.3.2 Site Discontinuation

The Sponsor has the right to close a site at any time. Reasons for closing a site may include, but are not limited to, the following:

- Excessively slow recruitment
- Poor protocol adherence
- Inaccurate or incomplete data recording

Pirfenidone—F. Hoffmann-La Roche Ltd

- Non-compliance with the International Conference on Harmonisation (ICH) guideline for Good Clinical Practice
- No study activity (i.e., all patients have completed the study and all obligations have been fulfilled)

5. ASSESSMENT OF SAFETY

5.1 SAFETY PLAN

Pirfenidone is currently approved for medical use in many countries of the world (see [Section 1.2](#)). The safety plan for patients in this study is based on clinical experience with pifenidone in completed and ongoing clinical studies and in post-marketing use. The anticipated important safety risks for pirfenidone are outlined below. Please refer to the pirfenidone *instruction for medical use of the medicinal product* for a complete summary of safety information.

Several measures will be taken to ensure the safety of patients participating in this study. Eligibility criteria have been designed to exclude patients at higher risk for toxicities. Patients will undergo safety monitoring during the study, including assessment of the nature, frequency, and severity of adverse events. In addition, guidelines for managing adverse events, including criteria for dosage modification and treatment interruption or discontinuation, are provided below.

5.1.1 Risks Associated with Pirfenidone

Pirfenidone has a favourable benefit-risk profile with a well-characterized long-term safety and tolerability profile and manageable side-effects. Pirfenidone does not appear to be associated with unexpected serious adverse events, which could be considered to be life-threatening. Guidelines for management of patients who develop the most common adverse events are provided in [Table 3](#) (see [Section 5.1.2](#)).

5.1.1.1 Gastrointestinal Adverse Events

Pirfenidone is associated with a dose response effect regarding gastro-intestinal side-effects notably nausea, vomiting, diarrhoea, dyspepsia. There is a correlation between the maximal plasma concentration of pirfenidone and the incidence of GI adverse events, suggesting that food may reduce the incidence of certain adverse events associated with pirfenidone.

Patients with clinically significant GI symptoms or disease will be excluded from this study (see [Section 4.1.2](#)).

Pirfenidone—F. Hoffmann-La Roche Ltd

5.1.1.2 Skin-Related Adverse Events

Common skin-related adverse events associated with pirfenidone are rash and photosensitivity. The seasonal variation in frequency of skin reactions suggests an association with sun exposure. The underlying mechanism of photosensitivity reactions is likely to be phototoxic and related to the drug ability to absorb both ultraviolet B and A. Pre-clinical data supports that pirfenidone-induced skin reactions are proportional to both light and drug exposure.

Exposure to direct sunlight (including sunlamps) should be avoided or minimised during treatment with pirfenidone. Patients should be instructed to use a sunblock daily, to wear clothing that protects against sun exposure, and to avoid other medicinal products known to cause photosensitivity. Patients should be instructed to report symptoms of photosensitivity reaction or rash to their physician. Severe photosensitivity reactions are uncommon.

5.1.1.3 Effects on Liver Function Tests

Elevations of ALT and AST $> 3 \times$ ULN have been reported in patients receiving therapy with pirfenidone. Rarely these have been associated with concomitant elevations in total serum bilirubin. Liver function tests (ALT, AST and bilirubin) should be conducted prior to the initiation of treatment with pirfenidone and subsequently as indicated in the schedule of assessments (see [Appendix 1](#)). Patients with significant signs of hepatic impairment will be excluded from the study (see [Section 4.1.2](#)).

In case of significant elevation of liver aminotransferases the dose of pirfenidone should be adjusted or treatment discontinued according to the guidelines provided in [Table 3](#). For patients with confirmed elevations in ALT, AST or bilirubin during treatment, the following dose adjustments may be necessary.

5.1.1.4 Cardiovascular Safety

The incidence of major cardiovascular events were similar between pirfenidone and placebo groups in pooled population of two clinical studies (ASCEND and CAPACITY). There is no evidence of pirfenidone having a significant effect on QT interval, incidence of arrhythmias and ischemia events. However, pirfenidone should be used with caution in patients treated with other moderate inhibitors of CYP1A2, such as amiodarone and propafenone.

Cardiac function should be monitored with ECG prior to the initiation of treatment with pirfenidone and subsequently as indicated in the schedule of assessments (see [Appendix 1](#)). Patients with clinically significant symptoms of cardiac disease will be excluded from the study (see [Section 4.1.2](#)).

Pirfenidone—F. Hoffmann-La Roche Ltd

5.1.1.5 Other Adverse Events

Dizziness

Dizziness has been reported in patients receiving pirfenidone. Patients should know how they react to the study drug before they engage in activities requiring mental alertness or coordination. In clinical studies, most patients who experienced dizziness had a single event, and most events resolved, with a median duration of 22 days.

Fatigue

Fatigue has been reported in patients receiving pirfenidone. Patients should know how they react to the study drug before they engage in activities requiring mental alertness or coordination.

Weight loss

Weight loss has been reported in patients treated with pirfenidone. There was an increase in anorexia and poor appetite but this was not consistently dose related. Investigator should monitor patients' weight, and when appropriate encourage increased caloric intake if weight loss is considered to be of clinical significance.

Risks which, were observed in the post-authorization setting:

- Angioedema
- Agranulocytosis

5.1.2 Management of Patients Who Experience Specific Adverse Events

Guidelines for management of specific adverse events are outlined in Table 3.

Table 3 Guidelines for Management of Patients Who Experience Specific Adverse Events

Event	Action to Be Taken
Gastrointestinal adverse events (nausea, vomiting, diarrhoea, dyspepsia)	
Confirm that the study drug is administered with food.
 
If symptoms persist when the drug is taken with food, the dose of pirfenidone should be reduced to 1-2 capsules (267-534 mg) 2-3 times/ day with food.
 
If symptoms resolve, the dose can be re-escalated to the recommended daily dose as tolerated.
 
If symptoms continue, treatment should be interrupted for 1-2 weeks to allow symptoms to resolve.
 
If symptoms continue after temporal interruption, treatment should be permanently discontinued.

Skin-related adverse events (photosensitivity reaction and rash)	
Mild to moderate photosensitivity reaction or rash - the dose of pirfenidone should be reduced to 801 mg (3 capsules) per day (267 mg (1 capsule) 3 times a day). Confirm that the patient uses a sunblock daily and avoids sun exposure.
 
If the rash persists after 7 days, pirfenidone should be discontinued for 15 days, with re-escalation to the recommended daily dose in the same manner as the dose escalation period.
 
Severe photosensitivity reaction or rash - treatment should be interrupted and medical advice is sought.
 
If the rash has resolved, pirfenidone may be re-introduced and re-escalated up to the recommended daily dose at the discretion of the investigator.

Elevations of ALT and AST	
ALT/ AST elevation > 3 to $\leq 5 \times$ ULN - confounding medicinal products should be discontinued, other causes excluded, and the patient monitored closely. If clinically appropriate, the dose of pirfenidone should be reduced or interrupted. Once liver function tests are within normal limits the dose may be re-escalated to the recommended daily dose if tolerated.
 
ALT/ AST elevation to $\leq 5 \times$ ULN accompanied by symptoms or hyperbilirubinaemia ($> 2 \times$ ULN) - treatment should be permanently discontinued.
 
ALT/ AST elevation to $> 5 \times$ ULN - treatment should be permanently discontinued.

Table 3 Guidelines for Management of Patients Who Experience Specific Adverse Events (cont.)

Event	Action to Be Taken
Increased QT Interval	
QTcF interval is > 500 ms and/ or > 60 ms longer than the baseline value, another ECG must be recorded, ideally within the next 5 minutes or in the utmost 24 hours, verified by a study site or local cardiologist.
 
If increase of QT Interval is confirmed, ECG monitoring should continue until QTcF has stabilized on two successive ECGs within 24 h, verified by a study site or local cardiologist. In this case study drug should be interrupted and the patient should be discontinued from study treatment.
 
If QTcF interval is between 500 and 550 msec, confirmed by a repeat ECG within 24 hours, and verified by a study site or local cardiologist, study treatment should be interrupted.
 
If an alternative explanation is identified (e.g., electrolyte abnormality or concomitant medication), re-initiation of study treatment may be considered by the investigator in consultation with the study medical monitor.

Dizziness	If dizziness does not improve within 3-4 weeks or worsens in severity, dose adjustment or even discontinuation of treatment may be warranted.
Fatigue	No action required.
Weight loss	If considered to be of clinical significance, increased caloric intake should be recommended to the patient.

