4.5.9 Electrocardiograms

Single ECG recordings will be obtained at specified timepoints, as outlined in the schedule of activities (see [Appendix 1](#)), and may be obtained at unscheduled timepoints as indicated.

All ECG recordings must be performed using a standard high-quality, high-fidelity digital electrocardiograph machine equipped with computer-based interval measurements. Lead placement should be as consistent as possible. ECG recordings must be performed after the patient has been resting in a supine position for at least 10 minutes. All ECGs are to be obtained prior to other procedures scheduled at that same time (e.g., vital sign measurements, blood draws, *bronchodilator test*) and should not be obtained within 3 hours after any meal. Circumstances that may induce changes in heart rate, including environmental distractions (e.g., television, radio, conversation) should be avoided during the pre-ECG resting period and during ECG recording.

For safety monitoring purposes, the investigator must review, sign, and date all ECG tracings. Paper and digital copies of ECG tracings will be kept as part of the patient's permanent study file at the site. The following should be recorded in the appropriate eCRF: heart rate, RR interval, QRS interval, PR duration, uncorrected QT interval, and QT interval corrected for heart rate using Fridericia's method (QTcF) based on the machine readings of the individual ECG tracings. Any morphologic waveform changes or other ECG abnormalities must be documented on the eCRF. If considered appropriate by the Sponsor, ECGs may be analyzed retrospectively at a central laboratory.

If at a particular postdose timepoint the QTcF is > 500 ms and/ or > 60 ms longer than the baseline value, another ECG must be recorded, ideally within the next 5 minutes or in the utmost 24 hours, and ECG monitoring should continue until QTcF has stabilized on two successive ECGs. The Medical Monitor should be notified. Standard-of-care treatment may be instituted per the discretion of the investigator. A decision on study drug discontinuation should be made, as described in [Section 5.1.2](#). The investigator should also evaluate the patient for potential concurrent risk factors (e.g., electrolyte abnormalities, co-medications known to prolong the QT interval, severe bradycardia).

4.5.10 6-Minute Walk Test

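### Protocol 5.1.2, Table 3: a confirmed QTcF above 500 and up to 550 ms falls under two conflicting instructions, one to discontinue study treatment and one only to interrupt it.

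*Protocol*

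**What the plan says.** The Increased QT Interval row of Table 3 (Protocol 5.1.2) has four paragraphs.

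1. Trigger: "QTcF interval is > 500 ms and/ or > 60 ms longer than the baseline value, another ECG must be recorded", within 24 hours at the latest and verified by a cardiologist.
2. On confirmation: "If increase of QT Interval is confirmed, ECG monitoring should continue until QTcF has stabilized on two successive ECGs within 24 h", again with cardiologist verification. The action follows: "In this case study drug should be interrupted and the patient should be discontinued from study treatment". No upper QTcF limit and no exception is given.
3. A narrower band: "If QTcF interval is between 500 and 550 msec, confirmed by a repeat ECG within 24 hours", and verified by a cardiologist. The action here is that "study treatment should be interrupted". Discontinuation is not mentioned.
4. If another explanation is found, such as an electrolyte abnormality or a concomitant medicine, "re-initiation of study treatment may be considered by the investigator in consultation with the study medical monitor". The paragraph does not say whether it qualifies paragraph 2, paragraph 3 or both.

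Three other sections touch the decision. Section 4.3.2 points to 5.1.2 for dose modification, interruption and discontinuation. Section 4.5.9 repeats the trigger, requires that the Medical Monitor be notified, and then says: "A decision on study drug discontinuation should be made, as described in" Section 5.1.2. Section 4.6.2 lists among the reasons for mandatory discontinuation: "Unacceptable tolerability and personal safety profile (e.g. adverse events listed in" Section 5.1.2.

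**The concern.** Paragraphs 2 and 3 overlap and give different actions. An investigator holding a confirmed QTcF inside the band can follow either and be within the protocol.

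This is an instruction for stopping treatment, so the first thing at stake is consistent handling of an individual patient. The second is coding. SAP 9.2 tabulates treatment-emergent events whose recorded action is permanent discontinuation (Tables 3.11.1 to 3.11.3). Whether a given ECG finding enters those tables could depend on which paragraph the site followed, and nothing in the planned outputs would show which one it was. The third is the label given to the patient in the complete case results, where the SAP separates those who received drug until Week 26 from those who stopped early but were followed.

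**Working it through.** No arithmetic applies. The check compares the conditions in the row and asks which paragraphs each kind of confirmed result meets. The inputs are the trigger in paragraph 1, the actions in paragraphs 2 and 3, and the re-initiation clause in paragraph 4. The 500 to 550 ms band is taken to include its limits, which the text does not state.

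| Confirmed result | Paragraph 2 (interrupt and discontinue) | Paragraph 3 (interrupt) | Conflict |
|---|---|---|---|
| QTcF above 500 and up to 550 ms | met | met | yes |
| QTcF above 550 ms | met | not met | no |
| Rise above 60 ms, QTcF below 500 ms | met | not met | no |
| QTcF exactly 500 ms, rise of 60 ms or less | not met | met | no |

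Take 520 ms as an example. It exceeds 500, so the trigger is met and, once confirmed, paragraph 2 applies. It also lies between 500 and 550, so paragraph 3 applies. The evidence required is the same under both: a repeat ECG within 24 hours and a cardiologist's verification. The route to confirmation therefore cannot separate the two rules.

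Next, whether another section decides between them. Sections 4.3.2 and 4.5.9 send the reader to 5.1.2 and contain no rule of their own for this case. Section 4.6.2 makes discontinuation mandatory for unacceptable tolerability and cites the 5.1.2 events as examples, but does not say which QTcF results qualify. All three lead back to the same row.

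Last, what the difference reaches in the analysis.

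- **Safety tables.** SAP 9.2 selects events by the recorded action with study drug. A permanent discontinuation is counted in Tables 3.11.1 to 3.11.3; an interruption is not.
- **Patterns 1 and 2.** Under SAP 6.3, both patterns consist of patients with a Week 26 FVC value: pattern 1 received drug until Week 26, pattern 2 stopped early and was followed. A patient who is interrupted, restarted and treated to Week 26 is pattern 1. The same patient, if discontinued and followed, is pattern 2. SAP 8.1 and Table 2.4 report the two separately within the complete case set.
- **Imputation.** SAP 6.3 imputes only for patterns 3 and 4, so moving a patient between patterns 1 and 2 calls for no imputed value. The observed Week 26 FVC enters the primary analysis under either label.

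**The case against.** The strongest defence is that the row can be read consistently. Table 3 gives guidelines. Its gastrointestinal and ALT/AST rows specify permanent discontinuation, while the skin row uses the word discontinued for a 15-day pause, so the unqualified word in the QT row need not mean a permanent stop. Paragraph 3 could be the specific case that overrides the general one, and paragraph 4 could qualify both.

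This shows that the sponsor may have had a coherent rule in mind, but the text does not state it. Paragraph 2 names interruption and discontinuation from study treatment as two actions in one sentence, and paragraph 3 names only the first. If both words meant a pause, the second would add nothing. No wording gives paragraph 3 priority or fixes the scope of paragraph 4.

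The defence on practical impact has more force, and most of it stands. Both paragraphs stop the drug on confirmation. Restart needs an alternative explanation and consultation with the medical monitor. Section 4.5.9 has the Medical Monitor notified of the triggering ECG, and Section 4.6.2 requires an immediate telephone report when early discontinuation is being considered. This central contact reduces the scope for sites to diverge, though it gives the monitor no rule to apply. Cases should also be few: Section 4.1.2 excludes a screening QTcF above 500 ms and any family or personal history of long QT syndrome, and Section 5.1.1.4 reports no evidence of a significant QT effect.

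Three stronger readings are tempting, and the documents do not support them.

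- A reader might infer that values above 550 ms have no instruction. They do: paragraph 2 has no upper limit and covers them alone.
- A reader might infer that the overlap disturbs the missing-data handling or the primary FVC result. It does not, because patterns 1 and 2 both have observed Week 26 values.
- A reader might infer that the rules are in the wrong order, since a rise above 60 ms with QTcF below 500 ms meets only the discontinuation paragraph. Absolute value and change from baseline are separate triggers that the documents do not rank, and ranking them is a clinical judgement.

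**Conclusion.** The row is inconsistent as written and should be corrected. The conflict is confined to a confirmed QTcF above 500 and up to 550 ms, and concerns whether treatment may be restarted, not whether it is stopped at first.

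The consequences are limited: management of the individual patient, the count of events leading to permanent discontinuation, and a descriptive split in one complete-case table. The documents give no expected number of such results. With approximately 60 patients and scheduled on-treatment ECGs at Weeks 4, 8 and 26 (and Week 52 for rollover patients), it is probably small. The case for correction rests on an ambiguous stopping instruction, not on bias in the efficacy estimate.

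The conclusion that the primary estimate is untouched assumes that a patient taken off drug still attends the Week 26 spirometry, as Sections 3.1 and 4.6.2 require. No view is taken on which of the two actions is clinically right.

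**What to change.** Reconcile the paragraphs of the QT row in Table 3 so that each confirmed QTcF result maps to exactly one action. State explicitly which results the re-initiation paragraph covers, and say whether discontinuation in this row is permanent, so that the recorded action with study drug is coded in the same way at every site. Sections 4.3.2, 4.5.9 and 4.6.2 can keep their references to 5.1.2 once the row is clear. Which action applies to which result is for the sponsor's medical team to decide.

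The cost is protocol wording only, by amendment or clarification letter. No change to the sample size, the visit schedule or the SAP methods is needed.
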